	Screening/Baseline Visit 1	Washout period	Visit 2 First Laser treatment (4 weeks +/- 5 days after baseline visit)	Visit 3 Second Laser Treatment (3 weeks +/- 5 days after first laser treatment)	Visit 4 Last day of topical treatment (4 weeks +/- 5 days after second laser treatment)
Procedures					
Informed Consent	X				
Inclusion/Exclusion criteria	X				
Demographic History Questionnaire	X				
Medical History Review	X				
Skincare History Review	X				
Evaluate Fitzpatrick skin type	X				
Evaluate baseline hyperpigmentation	X				
Urine dipstick test	X		X	X	X
Self assessment questionnaire	X				X
Standardized Digital photography	X		X	X	X
Adverse effects review	X		X	X	X
MoPASI evaluation	X		X	X	X
GAIS evaluation	X		X	X	X
Anesthetizing topical application			X	X	X
Protective goggles placed			X	X	
Laser treatment performed			X	X	
Exit Questionnaire					X

Potential participants will receive a thorough history and dermatologic physical exam to determine if patients meet the inclusion/exclusion criteria for being in the study. Urine dipstick tests will be performed on female

patients to confirm they are not pregnant. Consent will be obtained from eligible participants and will be enrolled in the study.

The study will be conducted over a 12 week period. There will be a 4 week washout period prior to laser treatments when the subjects will begin two skin care regimens, which are described below. Then there will be 2 laser treatments separated by 3 weeks. The subjects will continue the topical treatment 1 month after the 2nd laser treatment.

There will be 4 study visits: Baseline Visit 1, First laser treatment Visit 2 (4 weeks +/- 5 days after baseline visit), Second laser treatment Visit 3 (3 weeks +/- 5 days after first laser treatment), and Last day of topical treatment Visit 4 (4 weeks +/- 5 days after second laser treatment). During these visits, photographs of the participants' faces will be taken. Patient questionnaires will be given at baseline and at the end of the study.

Investigators will complete the study 4 months after subjects have completed their participation in the study.

8) Study Endpoints*

The study will reach endpoint for each patient either 1) once they have completed their exit survey after the 2 laser treatments and the topical treatments or 2) if they experience any adverse reactions from treatment and must be pulled from the study.

9) Procedures Involved*

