Local tolerability including itching, redness, burning, or pain will be assessed at each visit by the investigator. Subjects will also be asked to assess discomfort during treatment and also to maintain diary at home to record any side effects after each facial laser treatment. To lessen the probability of risks of laser treatment, will use the standard pulse energy and coverage known to produce the minimal amount of side effects, increase subject comfort, and allow for rapid healing.

Once all subjects have completed the study, one independent evaluator will retrospectively analyze the VISIA high definition photography data that was taken at each visit. The independent observer will evaluate the photos of each patient for clinical efficacy and tolerability using two validated grading scales (Modified Pigmentation Area and Severity Index (MoPASI) and Global Aesthetic Improvement Scale (GAIS)) at baseline and at weeks 5, 8, and 12.

The GAIS is used to evaluate change in aesthetics after intervention. 0 = worse, 1 = no change, 2 = improved, 3 = much improved, 4 = very much improved. The MoPASI is a dermatologist-developed modified scale derived from the validated Melasma area and severity index scale. Pigmentation is assessed in 4 sections of the facial skin, and three variables are assessed within each region: percentage of area involved, darkness of pigment in the area, and pattern of involvement in the area. Subjects will complete self-

assessment questionnaires at baseline and at the end of the study.

The Clear and Brilliant 1927nm laser has been used extensively in facial cosmetic surgery for skin resurfacing to improve the skin changes associated with photoaging and skin tone. The laser is FDA approved for this use (see Device attachments for documentation). The Solta Medical Company has proven that it produces safe and effective treatment and even in combination with topicals, has a high safety profile (see supporting documents).

Lytera 2.0 Correcting Serum, a Skin Medica product, is a non-hydroquinone, non-drug advanced Correcting Serum that has been proven to minimize the appearance of skin discoloration and dark spots. Our proposed study is to observe the effect of Lytera 2.0 on skin tone, and will not evaluate any underlying changes to skin structure or function. The assessments in the proposed study are observational and do not include biopsy or other method.

Key ingredients of Lytera 2.0 Pigment Correcting Serum:

Tranexamic Acid

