Phenylethyl Resorcinol

Niacinamide and Tetrapeptide 30

Marinen Extract blend

Phytic Acid

Other ingredients: Vitis Vinifera SCE, Plankton Extracts, Hydroxyacetophenone, Artemisia Capillaris, Marine Exopolysaccharides

Data that will be collected about subjects (see attached data collection form):

Age

Gender

Race

Past medical history including current and past illnesses, current medications, allergies, past surgeries, any past adverse effects to facial cosmetics, family history, social history including alcohol, tobacco, or illicit drug use.

Past skin care history including any surgical cosmetic procedures, fillers, injectables, lasers, or topical treatments.

Fitzpatrick skin type (I-IV)

Evaluation of baseline skin tone

Adverse effects experienced throughout the study

MoPASI scores

GAIS scores

Representative photographs of subjects at baseline and at subsequent visits

10) **Data and Specimen Banking***

Data will be stored on Box, a secure file sharing, storage, and collaboration system using a password-protected, encrypted laptop. Data will be stored for 1 year after the completion of the study. Only [name], principal investigator and [name] and [name], co-investigators and study coordinator will have access to the data. Data will only be released by Drs. [name] or [name] for publication of study results.

Stored data will include:

Age

Gender

Race

Past medical history including current and past illnesses, current medications, allergies, past surgeries, any past adverse effects to facial cosmetics, family history, social history including alcohol, tobacco, or illicit drug use.

Past skin care history including any surgical cosmetic procedures, fillers, injectables, lasers, or topical treatments.

Fitzpatrick skin type (I-IV)

Evaluation of baseline skin tone

Adverse effects experienced throughout the study

MoPASI scores

GAIS scores

Representative photographs of subjects at baseline and at subsequent visits

11) **Data Management***

Statistical analysis will be conducted to determine the effect size necessary to power a study. All statistical tests will be two-sided and interpreted at a 5% significance level. The primary analyses will be based on the MoPASI and GAIS scores. Scores after each laser treatment will be compared to baseline scores using the appropriate statistical test.

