Lytera 2.0 Pigment Correcting Serum does not contain any known teratogenic ingredients, however, the safety of the product has not been established in women who are pregnant, planning to be pregnant, or breastfeeding. While laser treatment is not recommended during pregnancy, it has not been shown to harbor any risks to the embryo. Patients will need to discuss risks vs benefits with their obstetricians. Subjects who become pregnant during study will not continue participation and will also be instructed to notify their obstetrician about their study participation.

15) Potential Benefits to Subjects*

Benefits to subjects are myriad, as combination topical and laser treatment is intended to moderately improve photo damaged and poor skin tone which can be distressing for patients. Facial cosmetic laser helps prevent and address early signs of aging skin, maintain younger-looking skin, and improve tone, texture and radiance. After even two treatments, patients can expect to have more uniform skin tone, improved texture, more radiant skin, minimized pore size appearance, and skin that looks and feels clear. The skin will continue to improve for several months following treatment.

16) Vulnerable Populations*

We will not be investigating any vulnerable populations. Once again, we will not include pregnant females in the study as skin changes that may be seen in pregnancy may influence the results of the study.

17) Sharing of Results with Subjects*

Results of study will be shared with subjects if they are interested in knowing results. This will be shared over the phone after the data has been analyzed.

18) Setting

Research will be conducted in the Facial Plastic and Reconstructive Surgery Department at the Professional Arts Center at the University of Miami Health System.

19) Resources Available

The principal investigator is a double board certified physician by the American Academy of Otolaryngology and the American Academy of Facial Plastic and Reconstructive Surgery. She has been in practice in Miami for over a decade and is thus very familiar with the population seeking skin care options for photo damage. One of her areas of expertise includes laser treatments for scars and facial rejuvenation. She already uses the laser specific to our study in her practice and is thus quite familiar with it. The secondary investigator is a third year Otolaryngology resident with

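### GAIS rates change, yet it is scored at Visit 1 and, as a primary scale, is to be compared only with that score; the between-arm comparison that the hypothesis needs is not specified

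*Combined protocol and SAP*

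**What the plan says.** Section 9 (Procedures Involved) describes the scale in these words: "The GAIS is used to evaluate change in aesthetics after intervention. 0 = worse, 1 = no change, 2 = improved". Grades 3 and 4 stand for larger improvement. The same section has one independent evaluator grade the photographs for MoPASI and GAIS "at baseline and at weeks 5, 8, and 12". In the Section 7 (Study Timelines) schedule, the row "GAIS evaluation" is marked at all four visits, including Visit 1. The text below it confirms that Visit 1 is the baseline visit: "There will be 4 study visits: Baseline Visit 1, First laser treatment Visit 2".

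Section 11 (Data Management) states: "The primary analyses will be based on the MoPASI and GAIS scores". It continues: "Scores after each laser treatment will be compared to baseline scores using the appropriate statistical test". It gives the purpose as: "Statistical analysis will be conducted to determine the effect size necessary to power a study". Tests are two-sided at the 5% level.

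The hypothesis in Section 2 (Objectives) is comparative: laser plus brightening cream against laser plus non-brightening cream. Both arms receive two laser treatments. Section 5 gives 7 subjects per arm.

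**The concern.** At Visit 1 neither the skin care regimen nor the laser has begun, so a scale that rates change after intervention has nothing to rate. Comparing later scores with baseline makes sense for a severity score such as MoPASI. For GAIS the later score is already the comparison with baseline.

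Taken literally, the Section 11 rule therefore asks whether skin improved at all, and the laser is expected to produce improvement in both arms. Section 15 (Potential Benefits) says as much: "After even two treatments, patients can expect to have more uniform skin tone, improved texture". A significant GAIS result could then appear whether or not the serum adds anything.

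Two things are at stake. One of the two primary scales may not address the hypothesis. The pilot may also fail to report the quantity it was run to supply, because an effect size for planning a trial of this hypothesis is a difference between arms.

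**Working it through.** **Inputs from the protocol.** 7 subjects per arm (Section 5); two-sided 5% tests (Section 11); GAIS graded 0 to 4 with 1 meaning no change (Section 9); photographs at Visits 2 and 3 taken before that day's laser (Section 9), so only Visits 3 and 4 are post-laser. The protocol states no power, effect size or GAIS distribution, so there is no figure of its own to reproduce.

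**What the stated comparison becomes.** If Visit 1 is scored in keeping with the legend, it is 1 for every subject. Post-laser score minus baseline score is then GAIS − 1, and testing that difference against zero is a one-sample test of GAIS against no change. Applied within an arm or to all subjects together, it contains no contrast between arms.

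**Illustration.** Assumptions, not protocol figures: the serum has no effect; in both arms a proportion π of subjects improves by one grade and the rest do not change; exact tests are used (the plan does not name a test).

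*Test against no change, unchanged subjects dropped.* With k subjects improved and none worse, the exact two-sided signed-rank p-value is 2/2^k.
- k = 5: 2/32 = 0.0625.
- k = 6: 2/64 = 0.031.
- At least 6 of 7 improved is therefore needed. The chance of a significant result in one arm is P(Bin(7, π) ≥ 6) = 7π⁶(1 − π) + π⁷ = a.

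*Test against no change, unchanged subjects counted as non-improvers.* By an exact sign test, 6 of 7 gives p = 0.125 and 7 of 7 gives 2/2⁷ = 0.016. All seven must improve, so the chance is π⁷.

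*Exactly one arm significant.* With independent arms, 2a(1 − a), using the first test.

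*Between-arm test.* With two grades observed, the exact rank test is equivalent to Fisher's exact test. The probability of p ≤ 0.05 is summed over all pairs of outcomes.

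| π (both arms) | Lytera arm significant, unchanged dropped | Lytera arm significant, unchanged as non-improvers | Exactly one arm significant (unchanged dropped) | Between-arm test significant |
|---|---|---|---|---|
| 60% | 15.9% | 2.8% | 26.7% | 1.1% |
| 70% | 32.9% | 8.2% | 44.2% | 0.7% |
| 80% | 57.7% | 21.0% | 48.8% | 0.2% |
| 90% | 85.0% | 47.8% | 25.5% | 0.02% |

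A single example shows the same thing. If 6 of 7 subjects improve by one grade in each arm and the seventh is unchanged, each arm gives p = 0.031 against no change (unchanged subjects dropped), while the between-arm test gives p = 1.0.

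**What 7 per arm can show.** With two grades observed, 6 of 7 against 1 of 7 gives a Fisher p-value of 2 × (49 + 1)/3432 = 0.029. Splits close to that extreme are needed for significance, so the estimate and its interval matter more than the p-value.

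**The case against.** The strongest reply is that Section 11 does not exclude a between-arm test. It leaves the test open and does not say whether the comparison with baseline is within arm, pooled, or a comparison of change between arms. The last reading fits the randomised design and the hypothesis. With Visit 1 fixed at 1, a between-arm test of change is identical to a between-arm test of the follow-up GAIS scores, because the constant cancels. This stands. A reader might infer that the plan commits itself to an analysis that ignores the control arm. The documents do not support that: the between-arm comparison is missing, not ruled out.

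A reader might also infer that the Visit 1 rating would corrupt the data. That is not supported either. The legend makes 1 the natural entry, and a constant 1 does no numerical harm. The data collection form mentioned in Section 9 was not available and may settle the entry, although it cannot make the entry informative.

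Three further objections are fair in part. The percentages in one arm are the chance of detecting an assumed real laser effect, not an error rate of a named analysis, and they depend heavily on how unchanged subjects are treated. The Section 15 expectation refers to two treatments, so it bears on Visit 4; the Visit 3 photograph follows only one. And MoPASI also lacks a stated between-arm contrast. What is particular to GAIS is that its baseline score has no meaning.

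Finally, this is a pilot and the GAIS scores are kept, so a between-arm estimate can still be computed. That makes the defect easy to repair. It does not supply the missing specification.

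**Conclusion.** The point holds in a limited form and should be fixed. The Visit 1 GAIS score is uninformative by the scale's own definition. The one comparison that Section 11 states for this primary scale, read literally, is a test against no change, and laser alone can make that significant in both arms. The between-arm comparison required by the hypothesis and by the planned effect size is left unspecified.

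Under the stated assumptions (7 per arm, no serum effect, 60% to 90% improving by one grade), the Lytera arm is significant against no change in 16% to 85% of trials, or 3% to 48% under the stricter counting. With unchanged subjects dropped, exactly one arm is significant in about 25% to 49%, which would invite a mistaken claim for or against the serum. The direct between-arm test is significant in about 1% or fewer. The conclusion about what the comparison tests follows from the text and does not depend on these rates.

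**What to change.** - **Sections 7 and 9:** delete the Visit 1 GAIS rating from the schedule and from the wording on grading times. State that every later GAIS rating is made against the Visit 1 photograph.
- **Section 11:** limit the comparison of scores with baseline to MoPASI. Compare follow-up GAIS directly between arms at one named primary visit, for example Visit 4 with Visit 3 supportive, using an exact ordinal rank test such as Wilcoxon-Mann-Whitney.
- **Effect size:** report a between-arm estimate with a 95% interval. One option is the probability that a Lytera subject is rated higher than a placebo subject, with ties counted as half.
- **Test against no change:** keep it, if wanted, as supportive only, labelled as within arm or pooled.

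The missing between-arm contrast for MoPASI comes from the same Section 11 sentence and should be handled once, as a separate point.

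The cost is one schedule cell, small edits in Section 9 and a few sentences in Section 11. One rating per subject is removed, and no visit, photograph or data collection is added.

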- Willing to refrain from using any other topical products on the face, systemic retinoids, or steroids, facial peels or other facial laser procedures throughout the duration of the study
- Willing to refrain from any cosmetic procedure including but not limited to facial surgery, dermal fillers, and neuromodulators for the duration of the study
- Willing to use only the facial skin care product regimen provided for the study
- Willing to avoid extended periods of sun exposure and the use of tanning beds during the study
- Willing to have photographs taken of the face to be used de-identified in evaluations, publications, and presentations
- For females: proof that they are not pregnant (urine pregnancy test)
- English-speaker

Exclusion criteria:

- Has any uncontrolled systemic disease (such as autoimmune disorders and

connective tissue disorders such as lupus erythematosus or Sjogren's syndrome
Has any active infection in face
Has history of any skin conditions that could interfere with treatment
Has used self-tanner recently
Is currently participating in another drug research study
Is NOT willing to refrain from using any other topical products such as skin lightening, retinoids, alpha/beta-hydroxyl acids, salicylic acid, vitamins C or D, steroids, or antibiotics on the face or systemic retinoids, steroids, facial peels, neuromodulators, dermal fillers, facial surgery, or other facial laser procedures throughout the duration of the study
For females: is pregnant
Non English-speaker

Individuals will be screened for eligibility via questionnaires that address each of the inclusion and exclusion criteria. Our final study sample will include the subjects who met the inclusion/exclusion criteria and did not voluntarily drop out of the study or develop adverse effects that prohibited them from safely completing the study. We will exclude adults unable to consent, patients under the age of 18, pregnant women, and prisoners.

5) Number of Subjects*

After recruiting our subjects, 14 patients will be randomized into either arm of the study (7 in each arm).

6) Study-Wide Recruitment Methods*

This is a single center study. We will recruit subjects from a clinical database of the practice of [name]. We will use several recruitment methods including invitation via a scripted email providing information describing the study protocol and end-points, scripted invitation telephone calls, and flyers.

7) **Study Timelines***

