One month prior to laser treatments (washout period), 14 male and female subjects with moderate hyper pigmentation and photo damage of the face will be randomized to 2 skincare regimens.

The regimens are:

- "Placebo arm" – Basic skin care regimen* (Facial Cleanser, TNS ceramide Treatment Cream (standard post-procedure moisturizer), and Essential Defense Mineral Shield Broad Spectrum SPF35 (all-physical sunscreen))
- "Lytera arm" – Basic skin care regimen + **Lytera 2.0**, which will be added between the Facial Cleanser and TNS Ceramide Treatment Cream

*The basic skin care regimen is a standard regimen used in several skincare product experiments

After cleansing the face, the patients in the Lytera arm will apply one pump of the pigment-correcting serum in a circular motion to the entire face

including the forehead, cheeks, chin, nose, and neck with care to avoid the eyes. The Lytera 2.0 is applied prior to applying moisturizer and sunscreen.

On laser treatment days, patients will come into the office without having applied any topical cream that day. Lidocaine topical may or may not be applied over the face avoiding the eyes (lidocaine use will be at discretion of Principal Investigator), and patients will be given protective goggles to shield the eyes during laser treatment. Next, the laser wand is pressed to the face and passed over the skin in various horizontal and vertical directions. Treatment takes 20 to 30 minutes.

Standardized digital photographs will be taken at baseline and at each subsequent visit using the Canfield VISIA Complexion Analysis (VISIA-CA) camera system at the highest resolution in a consistent position. Pictures will be taken before laser treatments on Visit 2 and Visit 3.

The subjects will complete an exit questionnaire after completion of the study at their last study visit (Visit 4). Through the questionnaire, we will obtain information on subject satisfaction with the study as well as their opinion of how their skin has changed. We hope to use the responses to assess efficacy of our skincare regimen and to improve future related research protocols.

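### Two unranked primary scales at two post-laser visits leave open which result supplies the pilot's effect size

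*Combined protocol and SAP*

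**What the plan says.** Section 11 (Data Management) is the whole analysis plan. On outcomes it says "The primary analyses will be based on the MoPASI and GAIS scores". On timing and comparison it says "Scores after each laser treatment will be compared to baseline scores using the appropriate statistical test". On error control it says "All statistical tests will be two-sided and interpreted at a 5% significance level". It gives no order between the scales or the visits, no multiplicity adjustment and no rule for what would count as a positive result. The same section gives the purpose of the analysis as finding the effect size on which to power a study, and the protocol title calls the trial a pilot.

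Section 8 (Study Endpoints) does not supply a primary outcome. It describes when a patient's participation ends, whether by finishing or by withdrawal for an adverse reaction, and for the first case reads "The study will reach endpoint for each patient either 1) once they have completed their exit survey after the 2 laser treatments and the topical".

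On timing, Section 7 says "Then there will be 2 laser treatments separated by 3 weeks", and Section 9 says "Pictures will be taken before laser treatments on Visit 2 and Visit 3". Section 9 has one independent evaluator score the photographs on both scales "at baseline and at weeks 5, 8, and 12", once all subjects have finished. The hypothesis in Section 2 is a comparison between arms and names no scale or visit.

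**The concern.** A pilot that is meant to deliver an effect size needs one defined quantity to estimate. Here there are four candidates of apparently equal standing, and two of them (Visit 3) are measured before the treatment course is complete. The scales also measure different things: GAIS grades overall aesthetic change, while MoPASI grades the area, darkness and pattern of pigment. They can disagree, and nothing says which prevails.

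Section 12 adds to the exposure, because it has efficacy data based on scale scores reviewed after each visit. With no primary result named, the choice could be made with results in view. An effect size picked because it was the largest of four is biased upward. Since required sample size varies with the inverse square of the effect size, a later trial powered on it would be too small. If the 5% tests are also read as evidence of efficacy, the error rate across the set is not the 5% that applies to each test.

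**Working it through.** **Inputs from the documents.** Primary scales: 2 (Section 11). Laser sessions: 2 (Section 7). Arms: 2, with 7 patients each (Section 5). Level: 5% two-sided per test (Section 11). The plan gives no effect size, SD, power, correlation or overall error rate, so it has no figure of its own to reproduce beyond the 5% per test.

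**What each visit measures.** Regimens start at the beginning of the 4-week washout (Sections 7 and 9).

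| Visit | Weeks from baseline | Lasers before photograph | Weeks of topical |
|---|---|---|---|
| 2 | 4 | 0 | 4 |
| 3 | 4 + 3 = 7 | 1 | 7 |
| 4 | 7 + 4 = 11 | 2 | 11 |

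Only Visits 3 and 4 follow a laser. Visit 3 reflects one of two lasers and about 7 of 11 weeks of topical, allowing for the visit windows. Visit 4 alone reflects the full course.

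**Count.** 2 scales × 2 post-laser visits = 4 results for one between-arm comparison. Section 11 literally describes comparison with baseline; done within each arm, that is 4 × 2 = 8 tests.

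**Bias from carrying forward the best of four.** With 7 per arm, the standard error of a difference in means, in SD units, is √(2/7) = 0.535. The expected maximum of four independent standard normals is 1.029; with a common correlation ρ it is multiplied by √(1 − ρ). With no true effect:

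- ρ = 0: 0.535 × 1.029 = 0.55 SD
- ρ = 0.5: 0.55 × 0.707 = 0.39 SD
- ρ = 0.8: 0.55 × 0.447 = 0.25 SD

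One prespecified result has expectation 0. If each difference is divided by its own sample SD, as a reported effect size would be, simulation gives slightly more: 0.60, 0.43 and 0.27.

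**False-positive chance if any one of four between-arm tests sufficed.** For independent tests, 1 − 0.95⁴ = 18.5%. Simulated with equally correlated normal outcomes, 7 per arm, two-sample t-tests and 40,000 null trials:

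| Assumed correlation | t-tests | Exact rank tests |
|---|---|---|
| 0 | 18.8% | about 14% |
| 0.5 | 15.9% | about 11% |
| 0.8 | 11.8% | about 9% |

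The rank-test column comes from 4,000 trials with GAIS cut into five levels at assumed frequencies of 5, 20, 40, 25 and 10%. If all four results had to be significant, the chance would be 1% or less.

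**Literal within-arm reading.** For eight independent tests, 1 − 0.95⁸ = 33.7%. With assumed correlations of 0.3 to 0.9 between scales and between visits, the simulated figure falls from about 33% to 20%. These are for no change in either arm, which is not the situation the plan expects, since both arms receive laser. Half of the eight tests would compare GAIS with a baseline value, although GAIS is already a change score (1 means no change).

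**After a fix.** One scale at one visit is one test at 5%. Keeping all four with Bonferroni means 0.05/4 = 0.0125 each; at 7 per arm and 80% power, the detectable difference would rise from 1.63 to 2.06 SD.

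**The case against.** The strongest reply is that this is a 14-patient pilot. The documents contain no success rule and no confirmatory decision, so family-wise error is not the main quantity at risk. That stands, and it is why the effect-size problem comes first here. It does not remove the point: estimating an effect size requires one defined outcome at least as much as a test does, and the plan still labels these analyses primary and prescribes 5% tests.

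A reader might infer that the trial has four chances to be declared positive, with a true false-positive rate of 12% to 19%. The documents do not support that as a statement about the plan. They neither say that one favourable result suffices nor require all four. Section 11 specifies no between-arm test and leaves the method open, so both the four-test count and the t-tests are assumptions, and rank tests give lower figures. Likewise, the equal standing of Visit 3 and Visit 4 is read from the absence of any ranking; it is not stated.

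A reader might also see a flaw in the scales running in opposite directions. It has no bearing on two-sided tests.

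Finally, making MoPASI the only primary scale is a choice with a price. The objective covers skin tone and photoaging, and the background section counts fine wrinkles and roughness as part of photodamage. MoPASI scores pigment only. That objection stands and is carried into the fix.

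**Conclusion.** The concern holds as a gap in definition. Sections 8 and 11 leave four scale-by-visit results unranked, half of them measured after only one of two lasers, and do not say which provides the effect size the pilot exists to estimate. Choosing the most favourable would overstate a null effect by about 0.25 to 0.55 SD, assuming a common correlation of 0.8 to 0 and no true effect on any of the four.

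The error-rate figures are conditional. About 12% to 19% applies only under an any-one-of-four rule with between-arm t-tests at those correlations; the 34% for eight within-arm tests assumes independence and no change in either arm. The documents give no correlations and state neither rule. The case for Visit 4 as the primary time is clear from the schedule. The choice of scale is a judgement for the investigators. The point should be corrected, but given the pilot purpose it does not undermine the design.

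**What to change.** In Sections 8 and 11:

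- Name Visit 4 as the primary time, because it is the only assessment after both lasers and the full topical course. Make Visit 3 secondary.
- State that the primary analysis compares the arms, using the independent evaluator's photograph scores. The visit table in Section 7 also lists both scales at each visit, so the source needs naming.
- Name one primary scale. The suggested option is MoPASI change from Visit 1 to Visit 4, which has a usable baseline, with GAIS at Visit 4 as key secondary. Alternatively, keep both scales at Visit 4 in a fixed testing order, the second tested at 5% only if the first is significant.
- State that the effect size for the later study comes from this primary result, reported with its confidence interval.

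This changes wording only and needs no new data. The costs are that a Visit 3 or secondary-scale result can no longer carry the conclusion alone, and that a MoPASI-only primary leaves non-pigment photoaging (fine wrinkles, roughness) to the secondary analysis. If that narrowing is unacceptable, the fixed order for both scales is the better choice.
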